2.3.1.2 Sensitivity analysis for primary endpoint

An ITT analysis, where multiple imputation (MI) will be used to impute missing outcomes for all randomized subjects with missing data, will be used as a sensitivity analysis. Information on the MI analysis is included in Section 2.9.

Statistical Analysis Plan

The primary endpoint will also be analyzed based on available data for the mITT and PTE populations, using a two-sided Z-Test with unpooled variance at the significance level of 0.05.

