5.6 Subject Withdrawal and Discontinuation

Each subject meeting all general and screening eligibility criteria shall remain in the clinical investigation until completion of the required follow-up period; however, a subject's participation in any clinical investigation is voluntary and the subject has the right to withdraw at any time without penalty or loss of benefit. Conceivable reasons for discontinuation may include, but not be limited to, the following:

- Subject death
- Subject voluntary withdrawal
- Subject lost-to follow-up as described below
- Subject's follow-up is terminated according to Section 3.3
- Subject's neurostimulation system has been explanted
- Subject becomes pregnant
- Subject fails to comply with the protocol requirements

Sites must notify the Sponsor of the reason(s) for subject discontinuation. Investigators must also report this to their respective IRB/EC as defined by their institution's procedure(s).

No additional follow-up is required or data recorded from subjects once withdrawn from the clinical investigation, except for the status (deceased/alive).

However, if a subject withdraws from the investigation due to problems related to the safety or performance of the study device, the investigator shall ask for the subject's permission to follow his/her status/condition outside of the clinical investigation.

In case of subject withdrawal of consent, the site should make attempts to schedule the subject for a final clinical investigation visit. At this final follow-up visit, the subject will undergo the following assessments:

- Review of adverse events
- Administration of patient reported outcomes

Lost-to-Follow-up

If the subject misses two consecutive scheduled follow-up time points and the attempts at contacting the subject detailed below are unsuccessful, then the subject is considered lost-to-follow-up. Site personnel shall make all reasonable efforts to locate and communicate with the subject (and document these efforts in the source documents), including the following, at each contact time point:

This confidential document is the property of Abbott and shall not be reproduced, distributed, disclosed or used without the express written consent of Abbott

Clinical Investigation Plan

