2.0 ANALYSIS CONSIDERATIONS

2.1 Analysis Populations

The analysis populations include:

1. Intention-to-Treat (ITT) Population: includes all randomized subjects. Subjects will be analyzed according to the treatment group they are randomized to. The ITT population will be used as the primary analysis population for the primary endpoint.
2. Modified Intention-to-Treat (mITT) Population: includes all randomized subjects except for those who are randomized to the SCS group who fail the trial period, do not receive a permanent system implant. Subjects will be analyzed according to the treatment group they are randomized to.
3. Per-Treatment Evaluable (PTE) Population: includes all subjects in the mITT population who either receive permanent implant or receive CMM. Subjects will be analyzed according to the actual treatment received. The PTE population will be used as the primary analysis population for the study except the primary endpoint analysis.

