2.3 Endpoint Analysis

2.3.1 Primary Endpoint

The primary effectiveness endpoint is the difference in response rates between groups at 6 months. A subject is considered a responder for the primary endpoint if the following criterion is met:

Improvement in pain, defined as a $\geq 50\%$ decrease on NRS.

2.3.1.1 The Hypothesis Test:

$$H_0: P_{SCS} = P_{CMM}$$

$$H_a: P_{SCS} \neq P_{CMM}$$

P_{SCS} and P_{CMM} denote the response rate at 6 months for SCS and CMM groups, respectively.

The ITT population defined in Section 2.1 will be used as the primary analysis. Trial failures (defined as having $< 50\%$ decrease in pain on the NRS from baseline to the end of the trialing, and who withdrew from the study per CIP), will be counted as non-responders in this analysis. All other subjects must complete their 6-month visit and have available primary endpoint data to be included in the primary analysis.

The response rates between the two groups will be compared using a two-sided Z-test with unpooled variance at the significance level of 0.05.

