2.9 Handling of Missing Data

As discussed in Section 2.3.1.2, for a sensitivity analysis of the primary endpoint, subjects with missing primary endpoint outcomes will have their outcomes imputed with multiple imputation (MI). PROC MI in SAS will be used to multiply impute missing outcomes. Multivariate imputations by fully conditional specification (FCS) methods with 20 burn-in interactions before each imputation, and the number of imputations equal to the percentage of missing data, and a seed of 8684915 will be used for analysis. If FCS methods fail to converge, other methods will be explored for the MI model.

The model may include, but not be limited to, the following predictors:

- Randomization group
- Age
- Sex at birth
- Lower back NRS at baseline and 3 months
- Duration of pain

If the model does not converge with this list of predictors, predictors will be removed from the model as needed to ensure convergence.

Once multiply imputed datasets have been generated, each imputation will be analyzed with standard statistical analyses before being combined for inferential analyses using PROC MIANALYZE. Example code which may be used is included in Appendix B.

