7.0 APPENDICES

APPENDIX A: EXAMPLE SAS CODE FOR MULTIPLE IMPUTATION

APPENDIX B: STATISTICAL ANALYSIS PLAN REVISIONS

This section documented changes in version number, revision details and rationale of SAP revisions. Administrative changes such as document date changes, reference numbering, editorial and grammatical changes are not captured.

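### The SAP does not carry the non-responder rule for trial failures into the multiple-imputation sensitivity analysis; read literally, that analysis moves the SCS rate towards the mITT result

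*SAP*

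**What the plan says.** SAP 2.3.1.1 divides the ITT population in two for the primary analysis. Trial failures are SCS subjects whose NRS fell by less than 50% by the end of trialing and who withdrew; they "will be counted as non-responders in this analysis". For the rest, "All other subjects must complete their 6-month visit and have available primary endpoint data to be included in the primary analysis".

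SAP 2.3.1.2 then specifies an ITT sensitivity analysis in which "multiple imputation (MI) will be used to impute missing outcomes for all randomized subjects with missing data". SAP 2.9 repeats that scope for subjects whose primary outcome is missing. It lists possible predictors (randomized group, age, sex, low-back NRS at baseline and 3 months, duration of pain) and leaves the list open to additions. Neither section mentions trial failures.

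Three other places bear on the point:

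- Protocol 5.6: "No additional follow-up is required or data recorded from subjects once withdrawn from the clinical investigation", apart from vital status.
- SAP 2.1: the mITT population "includes all randomized subjects except for those who are randomized to the SCS group who fail the trial period".
- SAP 2.9 on the code: "Example code which may be used is included in Appendix B". Section 7.0 instead has the heading "APPENDIX A: EXAMPLE SAS CODE FOR MULTIPLE IMPUTATION" and gives Appendix B to SAP revisions. No code appears in the available text.

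**The concern.** The sensitivity analysis should show whether the primary result survives the dropouts that the primary analysis leaves out. To do that cleanly, it should change only the handling of those dropouts.

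Read literally, it changes two things. It imputes the other dropouts, and it also replaces the assigned non-response of trial failures with imputed outcomes. A withdrawn trial failure has no 6-month NRS and would normally have no 3-month NRS. Neither trial result nor implant status is a listed predictor. Permanent implant requires a successful trial (Protocol 6.5 and 6.5.4), so the SCS subjects with observed 6-month outcomes are mainly implanted trial successes. Trial failures would be imputed at roughly their response rate.

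The mITT analysis removes these same subjects. An analysis labelled ITT would therefore drift towards mITT in the SCS arm, and its agreement with the primary result would be harder to interpret. Two analysts could also obtain different answers from the same SAP.

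**Working it through.** **Inputs from SAP 2.4.** Phase I has 200 subjects randomized 3:2, so 120 SCS and 80 CMM. With 25% attrition, 90 and 60 are evaluable. Response rates are 45% and 20%, and the test is a two-sided unpooled Z-test at 0.05.

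**The plan's own figure.** SE = √(0.45×0.55/90 + 0.20×0.80/60) = 0.0736. Power = Φ(0.25/0.0736 − 1.96) = Φ(1.437) = 92.5%. The stated power of at least 90% is reproduced.

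**Assumptions not in the documents.**

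- F trial failures lie among the 90 evaluable SCS subjects. The SAP does not say whether its attrition figure includes them.
- F is 5 to 10. The SAP gives no rate. Table 1 assumes about 80 SCS subjects in the PTE population, against 90 evaluable, which leaves about 10. That gap may also reflect rounding or trial successes who did not proceed to implant.
- The 45% is the primary ITT rate, that is 40.5 responders of 90.
- The other 30 SCS dropouts are non-informative, and only the listed predictors enter the model.

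**Formulas.**

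- Response rate among observed SCS subjects who are not trial failures: q = 40.5/(90 − F). This is also the mITT available-data rate.
- Literal reading: (40.5 + F×q + 30×q)/120 = q.
- Rule kept: (40.5 + 30×q)/120.
- Difference: F×q/120.

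| F | Literal | Rule kept | Difference |
|---|---|---|---|
| 5 | 40.5/85 = 47.6% | (40.5 + 14.29)/120 = 45.7% | 2.0 points |
| 10 | 40.5/80 = 50.6% | (40.5 + 15.19)/120 = 46.4% | 4.2 points |

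If 45% is instead taken as the rate in implanted subjects, the difference is F×0.45/120, or 1.9 points for F = 5 and 3.8 for F = 10.

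**Check by simulation.** Fully conditional imputation was simulated with the listed predictors only (80 simulated trials, 5 imputations and 10 burn-in iterations each). With 8.3% trial failures (10 of 120), the literal version gave an SCS rate of 50.8% and mITT gave 50.8%. With the rule kept it was 45.9%, against a primary rate of 45.4%.

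**Effect on the test, F = 10, CMM at 20%.** Using 90 and 60 as a rough allowance for imputation uncertainty, not Rubin's rules:

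- Primary: z = 0.25/0.0736 = 3.40, p = 0.0007.
- Literal: z = 0.306/0.0738 = 4.15, p < 0.0001.
- Rule kept: z = 0.264/0.0737 = 3.58, p = 0.0003.

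All three lead to the same conclusion.

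**The case against.** The strongest reply is that the SAP already answers the question. Section 2.3.1.1 gives trial failures an outcome and requires observed data only of everyone else. Section 2.3.1.2 follows directly, and 2.9 speaks of missing outcomes, not missing NRS values. A subject already classed as a non-responder need not count as missing. This reading is coherent and may be what the sponsor intends. However, the assignment is worded for the primary analysis, and no visible text extends it. The example code might settle the matter. Its absence from the available text is not a fault in the plan, and the appendix mismatch is editorial.

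A second reply also stands. The predictor list is open, and end-of-trial NRS is collected (Protocol 6.5.3). A predictor of trial failure in the model would pull the imputed rate for these subjects back down. The literal result therefore approaches mITT but need not equal it, and the simulation, which used only the listed predictors, does not test this.

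A reader might draw two stronger inferences that the documents do not support:

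- **That the sensitivity analysis must be more favourable to SCS than the primary.** Only the trial-failure component has a known direction. The imputed outcomes of other dropouts can move the estimate either way.
- **That the choice of reading could decide significance.** Disagreement at 0.05 can be constructed. For F = 10, with other SCS dropouts responding at 20% and CMM dropouts at 40%, p is 0.019 (literal) against 0.070 (rule kept) with n = 90 and 60. But the planned imputation has no step that would impose such rates, and with n = 120 and 80 the rule-kept p-value falls to 0.036, so the disagreement disappears.

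Finally, 2.3.1.2 also requires an mITT analysis, so readers can already see the effect of the trial-failure convention by comparing it with the primary.

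**Conclusion.** The point holds as an unresolved ambiguity in a sensitivity analysis, and one of its two readings gives a less useful analysis. On the literal reading, the SCS rate is about 2 to 4 points higher than with the rule kept. That size rests on an assumed 5 to 10 trial failures among 90 evaluable SCS subjects, the SAP's 45%, non-informative other dropout and the listed predictors only. The documents give no basis for larger numbers of failures.

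Under the SAP's assumed rates the conclusion at 0.05 is the same either way. The primary test treats trial failures explicitly, and the success criterion in SAP 2.7 depends only on that test. This is a cheap improvement that should be made, at the low end of that grade.

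**What to change.** Add to SAP 2.3.1.2 and 2.9: *Trial failures as defined in 2.3.1.1 remain non-responders in every imputed data set; only other missing 6-month outcomes are imputed.* Make the example code follow the same rule and correct the appendix reference in 2.9. If imputing trial failures is intended, say so and describe the result as close to mITT in the SCS arm.

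The change should be made while SAP 1.6 still keeps outcomes by arm from the sponsor's statisticians. It costs one sentence in two sections and a check of the code, and the primary test does not change. The downside for the sponsor is that the sensitivity estimate may be slightly less favourable to SCS.

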2.4 Sample Size/Power Calculations

The study was designed to enroll approximately 200 subjects in Phase I and up to 70 subjects in Phase II. The following assumptions are used in the power calculation for the primary endpoint:

- Assumed response rate of 45% for the SCS group and 20% for the CMM group
- 3:2 (SCS:CMM) randomization ratio
- 25% attrition rate to primary endpoint (6 months) follow-up in both groups
- Two-sided alpha of 0.05
- Z-test with unequal variance

Based on the assumptions above, there is at least 90% power to evaluate the primary endpoint with the Phase I cohort.

The minimum detectable differences for secondary endpoints using phase I PTE cohort (assume approximately 80 SCS and 60 CMM) with 80% power are shown in Table 1 below.

Table 1: Minimum Detectable Differences (MID) for Secondary Endpoints

Secondary Endpoints	MID (standard deviation for each group)
#1: Composite Responder	23%
#2: Relative NRS Change in %	16.9(35)
#3: ODI Change	7.2 (15)
#4: PCS Responder	21%
#5: PGIC (%)	23%
#6: Relative Pain Interference Change in %	7.2 (15)
#7: Relative Physical Function Change in %	12.0 (25)

The sample size re-estimation will be based on the interim analysis (IA) population (Adaptive Design Plan CL1014964). The unblinded independent statistician will perform the sample size re-estimation for 4 endpoints (1 primary and secondary endpoints #1, #2, and #3) and generate a recommendation if more subjects are needed to meet the statistical significance of each endpoint.

The power calculation was performed using PASS 15 (NCSS LLC).⁵

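### The sensitivity analyses of the primary endpoint never let dropouts do worse than missing at random predicts, and the mITT and PTE analyses can be expected only to raise the SCS–CMM difference

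*SAP*

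**What the plan says.** The primary analysis is labelled ITT. Under SAP 2.3.1.1, SCS subjects who fail the trial stimulation and withdraw count as non-responders; everyone else enters only with an available 6-month outcome. Apart from trial failures it is therefore an available-data analysis. SAP 2.4 plans for "25% attrition rate to primary endpoint (6 months) follow-up in both groups".

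SAP 2.12 adds no sensitivity analysis beyond SAP 2.3.1.2, which lists three:

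- MI for all randomised subjects with missing outcomes. SAP 2.9 specifies fully conditional specification, with candidate predictors of randomisation group, age, sex, low back NRS at baseline and 3 months, and duration of pain. If the model does not converge, "predictors will be removed from the model as needed to ensure convergence".
- mITT and PTE: "The primary endpoint will also be analyzed based on available data for the mITT and PTE populations".

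SAP 2.1 defines mITT as a set that "includes all randomized subjects except for those who are randomized to the SCS group who fail the trial period" or are not implanted. PTE is the part of mITT that received an implant or CMM, grouped by treatment received.

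Neither document lists a delta adjustment, tipping point, reference-based imputation or non-responder imputation for the remaining missing outcomes.

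**The concern.** A sensitivity analysis should ask whether the conclusion survives less favourable assumptions about what was not observed. The mITT and PTE analyses do not ask this. They use the same available data and, in the main, take scored SCS non-responders out of the denominator. MI does address the missing outcomes, but without a departure parameter it assumes that, given the predictors, dropouts resemble those who stayed. A subject who left before month 3 has no 3-month NRS and, with the listed predictors, is imputed from arm and baseline alone.

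Informative dropout is plausible. The trial is open-label (SAP 1.6), explant is a listed reason for discontinuation (CIP 5.6), and subjects unwilling to complete assigned treatment are to be withdrawn (CIP 6.6.4). With a quarter of outcomes potentially missing, a marginal result could be reported with two stronger supporting analyses and no statement of how far the missing outcomes would have to depart from the model to overturn it.

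**Working it through.** **Inputs (SAP 2.4).** "Assumed response rate of 45% for the SCS group and 20% for the CMM group"; "3:2 (SCS:CMM) randomization ratio"; about 200 subjects in Phase I; 25% attrition; two-sided 0.05; PTE of about 80 SCS and 60 CMM. Hence 120 SCS and 80 CMM randomised, and 120 × 0.75 = 90 and 80 × 0.75 = 60 evaluable.

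**Test.** z = (p₁ − p₂) / √[p₁(1 − p₁)/n₁ + p₂(1 − p₂)/n₂], unpooled as in SAP 2.3.1.1.

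**The plan's own figure.** At 45% vs 20% with 90 and 60: SE = 0.0736, z = 0.25/0.0736 = 3.40, power = Φ(3.40 − 1.96) = 92.5%. The stated power of at least 90% reproduces.

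**Assumption.** The SAP gives no count of trial failures. I split SCS as 80 implanted with data, 10 trial failures (90 evaluable less the planned PTE of 80) and 30 missing; CMM as 60 with data and 20 missing. Some trial failures may already be counted in the 25%, so this is only one reading.

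**Direction of mITT and PTE.** Removing F subjects scored as non-responders changes the SCS rate from r/n to r/(n − F), which can only be higher. At the design rates r = 0.45 × 90 = 40.5. Removing 5, 10, 20 or 30 moves the difference from 25.0 to 27.6, 30.6, 37.9 or 47.5 points.

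**A borderline result, with fixed responses filled in for the missing subjects.**

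| Scenario | SCS | CMM | z | p |
|---|---|---|---|---|
| Primary | 32/90 = 35.6% | 12/60 = 20.0% | 2.155 | 0.031 |
| mITT/PTE (10 trial failures removed) | 32/80 = 40.0% | 12/60 = 20.0% | 2.657 | 0.008 |
| Dropouts: SCS 7/30, CMM 4/20 | 39/120 = 32.5% | 16/80 = 20.0% | 2.020 | 0.043 |
| Dropouts: SCS 6/30, CMM 4/20 | 38/120 = 31.7% | 16/80 = 20.0% | 1.892 | 0.059 |
| Dropouts: SCS 5/30, CMM 4/20 | 37/120 = 30.8% | 16/80 = 20.0% | 1.763 | 0.078 |
| Dropouts: SCS 0/30, CMM 4/20 | 32/120 = 26.7% | 16/80 = 20.0% | 1.107 | 0.27 |
| Dropouts: SCS 0/30, CMM 0/20 | 32/120 = 26.7% | 12/80 = 15.0% | 2.055 | 0.040 |
| Dropouts: SCS 5/30, CMM 0/20 | 37/120 = 30.8% | 12/80 = 15.0% | 2.727 | 0.006 |

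With CMM dropouts at 20%, the tipping point lies between 7/30 and 6/30, that is, where SCS dropouts do no better than the CMM arm. These fills treat imputed outcomes as observed. Proper MI adds between-imputation variance, so they are approximate.

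**The same stress at the design rates.** With no SCS dropout responding and CMM dropouts at 20%: 40.5/120 = 33.75% vs 16/80 = 20%, z = 0.1375/0.0622 = 2.21. The result survives.

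**Direction of MI.** This was checked with a simulation of 400 replicates per scenario: 120 vs 80 subjects, about 25% dropout, 10 trial failures, and group, baseline NRS and 3-month NRS in the model. All outcome and dropout parameters are assumptions. The two MI figures keep trial failures as non-responders, or impute them.

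- Dropout unrelated to outcome: primary 23.4 points; MI 24.5 or 28.5.
- SCS dropouts worse at month 3: primary 31.5; MI 23.8 or 27.8, below the primary in 99% or 92% of replicates.
- The same dropout pattern in both arms: primary 26.6; MI 24.8 or 28.8.
- Only CMM dropouts worse at month 3: primary 17.0; MI 24.2 or 28.2.

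The mITT estimate was below the primary in none of the replicates of any scenario.

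**The case against.** A reader might infer that none of the three analyses can come out below the primary, so that MI merely repeats it. The documents do not support that. SAP 2.9 lists 3-month NRS as a predictor, and the simulation shows MI well below the primary when SCS dropouts were already doing badly at month 3. MI would come close to the primary by construction only if dropout were uninformative or nearly all of it preceded month 3, and the documents give no dropout timing.

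A reader might also infer that the convergence rule could remove randomisation group and shrink a 25-point effect to 0.75 × 25 = 18.75 points. The rule does protect no predictor, but a binary covariate with planned rates of 45% and 20% is an unlikely cause of non-convergence. The 18.75 also requires that no other predictor carries information on arm. Since 3-month NRS does, that figure is a worst case.

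Other points on the plan's side stand in part:

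- Scoring trial failures as non-responders already works against SCS.
- Subjects withdrawn under CIP 6.6.4 may well be dissatisfied CMM non-responders, whose exclusion also works against SCS. The borderline result stays significant when all missing subjects in both arms count as non-responders (p = 0.040), and strengthens if only CMM dropouts all fail (p = 0.006 with SCS at 5/30). Only dropout that is worse in SCS overturns it.
- mITT also drops non-implanted SCS subjects, and PTE can regroup or drop a few CMM subjects, so these sets do not strictly only remove scored non-responders. The bar on early crossover in CIP 6.6.4 should keep these routes small.
- SAP 2.3.1.2 uses the term sensitivity analysis in its text only for MI; mITT and PTE fall under the section heading. Relabelling them is a matter of clarity.

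What remains is that the single analysis of missing data has no version that departs from missing at random.

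**Conclusion.** The point holds in this form: mITT and PTE can be expected only to raise the SCS–CMM difference and say nothing about missing outcomes; MI is the one check on missing data, rests on missing at random and may go either way; no listed analysis lets dropouts do worse than their observed data predict.

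Its size depends on the result. At the design rates the conclusion is robust even to zero response among SCS dropouts. For a difference of about 15.6 points, under the assumed split, significance is lost when SCS dropouts respond at the CMM rate of 20%, while the mITT and PTE p-value is 0.008. This is a worthwhile improvement to the sensitivity analysis, not a defect in the primary test. The direction for mITT and PTE assumes that the subjects they remove are scored non-responders and that almost nobody changes arm before 6 months.

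**What to change.** In SAP 2.3.1.2 and 2.9:

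1. Add a delta-adjusted (tipping-point) version of the planned MI. Vary the imputed response separately in the SCS and CMM arms and report the combinations at which p crosses 0.05. Filling all missing outcomes as non-responses in both arms would not be enough, as the p = 0.040 case shows.
2. State that randomisation group is always kept in the imputation model, whatever else is removed for convergence.
3. State whether trial failures stay non-responders under MI. SAP 2.3.1.1 sets that rule for the primary analysis, and SAP 2.3.1.2 does not say whether it carries over. In the simulation with 10 trial failures the choice moved the estimate by about 4 points.
4. Describe mITT and PTE as supplementary analyses of different populations.

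The cost is SAP wording and a short extension of the MI program, with no new data collection. The downside is that the reported result may look less robust than under the current set.
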